9.4. Emergency Unblinding

This study is blinded; neither subjects nor investigators or site staff will be aware of subjects' treatment assignments. However, in the event of a medical emergency when knowledge of the treatment received is needed for medical management of an SAE, the investigator may unblind an individual subject's treatment allocation. When possible, prior to unblinding, the investigator should attempt discuss the reason for wanting to unblind with the Medical Monitor. Instructions for emergency unblinding are contained in the Procedures Manual (IRT/Suvoda, Site Safety Reporting Instructions).

9.5. Serious Adverse Event Reporting and Follow Up

SAEs will be collected from the time of the first dose of study drug until the EoS visit, or for at least 8 weeks following the infusion of study drug if the subject discontinues early. SAEs that are related to the investigational product and continue beyond the normal collection period will be followed until resolution or until stabilized. SAEs that begin after the defined collection period, but that the Investigator considers to be related to study drug, may be reported at any time.

All SAEs must be reported to the Sponsor or designee within 24 hours of clinical site personnel becoming aware of the event. Refer to the study Procedures Manual for SAE reporting requirements and details.

9.6. Suspected Adverse Reaction Definition

A suspected adverse reaction is any AE for which there is a reasonable possibility that the investigational product caused the AE. "Reasonable possibility" means there is evidence to suggest a causal relationship between the drug and the AE. The following criteria may be used as a guide for assessing causality:

Yes/Related

There is evidence exists to suggest a causal relationship between the drug and the AE, such as:

- An event that is uncommon and known to be strongly associated with drug exposure (e.g., angioedema, hepatic injury, Stevens-Johnson Syndrome)
- An event that is not commonly associated with drug exposure, but is otherwise uncommon in the population exposed to the drug (e.g., tendon rupture)

• No/Unrelated

Another cause of the AE is more plausible (e.g., due to underlying disease or occurs commonly in the study population), or a temporal sequence cannot be established with the onset of the AE and administration of the study treatment, or a causal relationship is considered biologically implausible.

9.7. Adverse Event Expectedness

An AE or suspected adverse reaction is considered "unexpected" if it is not listed in the ALPN-101 IB. The Sponsor or Medical Monitor is responsible for determining the expectedness of all reported SAEs, including serious suspected adverse reactions.

9.8. Adverse Events of Interest

The occurrence of an AEI whether serious or nonserious, must be immediately reported to AIS within \leq 24 hours of site awareness by entering the information into the electronic data capture (EDC) system, then completing an AEI narrative form and sending it to the following email address:

• [contact]

The AEI reporting period will begin at the time of first dose of study drug and continues until the final study day (i.e., EoS visit, or end of follow-up for subjects prematurely withdrawn).

Recommendations regarding the medical management of AEIs can be found in §8.1.

AEIs are listed below:

- IRRs (see §9.8.1)
- Oral mucocutaneous lesions (including aphthous ulcers) not attributed to SLE (see §9.8.2)
- Infections Grade ≥ 3 (see §9.8.3)

9.8.1. Infusion-related Reactions

Terminology and Grading of IRRs

The term "IRR" should generally be used and the severity assessed per CTCAE v5.0. More specific terms should only be used when the mechanism and/or diagnosis can be definitively determined. For instance, "anaphylaxis" should only be used for events fitting the criteria in Table 4, while "cytokine release syndrome" should be used for fitting the description in Table 5 and determined to be in association with the release of cytokines.

An allergic reaction which occurs in relationship to study drug administration should be reported as an IRR. Each sign or symptom of the reaction should be recorded as an individual AE. If multiple signs or symptoms occur with a given infusion-related event, each sign or symptom should be recorded separately with its level of severity.

Table 4 NIAID/FAAN Clinical Criteria for Diagnosis of Anaphylaxis

An	aphylaxis is highly likely when any one of the three following criteria are fulfilled:
1.	Acute onset of an illness (minutes to several hours) with involvement of the skin, mucosal tissue, or both (e.g., generalized hives, pruritus or flushing, swollen lips-tongue-uvula) and at least one of the following:
	• Respiratory compromise (e.g., dyspnea, wheeze-bronchospasm, stridor, reduced PEF, hypoxemia)
	• Reduced BP or associated symptoms of end-organ dysfunction (e.g., hypotonia [collapse], syncope, incontinence)
2.	Two or more of the following that occur rapidly after exposure to a likely allergen for that patient (minutes to several hours):
	• Involvement of the skin-mucosal tissue (e.g., generalized hives, itch-flush, swollen lips-tongue-uvula)
	• Respiratory compromise (e.g., dyspnea, wheeze-bronchospasm, stridor, reduced PEF, hypoxemia)
	• Reduced BP or associated symptoms (e.g., hypotonia [collapse], syncope, incontinence)
	Persistent gastrointestinal symptoms (e.g., crampy abdominal pain, vomiting)
3.	Reduced BP after exposure to known allergen for that patient (minutes to several hours):
	• Infants and children: low systolic BP (age specific) or greater than 30% decrease in systolic BP*
	• Adults: systolic BP of less than 90 mm Hg or greater than 30% decrease from that person's baseline
	, Blood pressure; NIAID/FAAN, National Institute of Allergy and Infectious Diseases/Food Allergy and Anaphylaxis twork; PEF, Peak expiratory flow.
	ow systolic BP for children is defined as $< 70 \text{ mm}$ Hg from 1 month to 1 year, $< (70 \text{ mm}$ Hg + $[2 \text{ x age}])$ from 1 to 10 ars, and $< 90 \text{ mm}$ Hg from 11 to 17 years.

Table 5 AE Terms and Grades for Reporting IRRs

AE Term	Grade 1	Grade 2	Grade 3	Grade 4	Grade 5
Infusion	Mild transient	Therapy or infusion	Prolonged (e.g., not	Life-threatening	Fatal
Related	reaction;	interruption	rapidly responsive to	consequences;	
Reaction	infusion	indicated but	symptomatic	urgent intervention	
	interruption not	responds promptly	medication and/or	indicated	
	indicated;	to symptomatic	brief interruption of		
	intervention not	treatment (e.g.,	infusion); recurrence		
	indicated	antihistamines,	of symptoms		
		NSAIDs, narcotics,	following initial		
		IV fluids);	improvement;		
		prophylactic	hospitalisation		
		medications	indicated for clinical		
		indicated for	sequelae		
		\leq 24 hrs			
Definition: A dis	order characterized l	by adverse reaction to the	e infusion of pharmacolo	gical or biological sub	stances.

From (75)

Table 5 AE Terms and Grades for Reporting IRRs (Continued)

AE Term	Grade 1	Grade 2	Grade 3	Grade 4	Grade 5
Anaphylaxis			Symptomatic	Life-threatening	Fatal
			bronchospasm, with	consequences;	
			or without urticaria;	urgent intervention	
			parenteral	indicated	
			intervention		
			indicated; allergy-		
			related		
			edema/angioedema;		
			hypotension		
Definition: A disc	order characterized b	y an acute inflammator	y reaction resulting from	the release of histamin	e and
histamine-like su	bstances from mast	cells, causing a hyperser	nsitivity immune respons	e. Clinically, it present	ts with
breathing difficul	ty, dizziness, hypote	ension, cyanosis and los	s of consciousness and m	ay lead to death.	
Cytokine	Fever with or	Hypotension	Hypotension	Life-threatening	Fatal
release	without	responding to fluids;	managed with one	consequences;	
syndrome	constitutional	hypoxia responding	pressor; hypoxia	urgent intervention	
	symptoms	to $<40\% O_2$	requiring $\geq 40\% O_2$	indicated	
Definition: A disorder characterized by fever, tachypnea, headache, tachycardia, hypotension, rash, and/or hypoxia caused					
by the release of	cytokines.				

IRRs, Infusion-related reactions; NSAIDs, Nonsteroidal anti-inflammatory drugs; IV, Intravenous; O₂, Oxygen. From NCI-CTCAE v5.0.

9.8.2. Oral Mucocutaneous Lesions

Efforts should be made to determine the cause of oral mucocutaneous lesions (including aphthous ulcers) observed during the study (see §8.1.2).

Any oral mucocutaneous lesions attributed to underlying SLE (including new or worsening lesions) should not be reported as AEs, but should be recorded in SLEDAI-2K 30 (mucosal ulcers) and/or BILAG 2004 (mucosal ulceration—mild, or mucosal ulceration—severe, as appropriate consistent with glossary definitions) and/or CLASI (mucosal lesions). Treatment should be recorded as concomitant medications, listing SLE activity as the indication for treatment.

Any oral mucocutaneous lesions not attributed to SLE should be reported as AEIs and graded according to CTCAE (see §9.2). Whenever possible, the specific cause or type (e.g., thrush) should be reported. Aphthous ulceration, if not assessed as related to SLE, may be reported as "aphthous ulcer," "aphthous stomatitis" or other similar verbatim term as considered appropriate by the Investigator. However, in such cases when no specific term exists in CTCAE, the AE should be graded according to "mucositis oral" or "pharyngeal mucositis," as appropriate to the anatomical location of the lesion(s). Table 6 provides terms and for grading for some oral mucocutaneous lesions per CTCAE.

Note: For lesions reported as AEIs, photographic documentation should be collected at presentation and in the event of significant change (as detailed in the Procedures Manual).

 Table 6
 AE Terms and Grades for Reporting Oral Mucocutaneous Lesions

AE Term	Grade 1	Grade 2	Grade 3	Grade 4	Grade 5	
Mucositis, oral	Asymptomatic or mild symptoms; intervention not indicated	Moderate pain or ulcer that does not interfere with oral intake; modified diet indicated	Severe pain; interfering with oral intake	Life-threatening consequences; urgent intervention indicated	Fatal	
			flammation of the oral		1	
Pharyngeal mucositis	Endoscopic findings only; minimal symptoms with normal oral intake; mild pain but analgesics not indicated	Moderate pain, analgesics indicated; altered oral intake; limiting instrumental ADL	Severe pain; unable to adequately aliment or hydrate orally; limiting self care ADL	Life-threatening consequences; urgent intervention indicated	Fatal	
Definition: A d pharynx.	isorder characteriz	ed by ulceration or in	flammation involving t	he mucous membra	ne of the	
Mucosal infection	Localized, local intervention indicated	Oral intervention indicated (e.g., antibiotic, antifungal, or antiviral)	IV antibiotic, antifungal, or antiviral intervention indicated; invasive intervention indicated	Life-threatening consequences; urgent intervention indicated		
Definition: A d	isorder characteriz	ed by an infectious pr	ocess involving a muco	osal surface.		
Pharyngitis		Oral intervention indicated (e.g., antibiotic, antifungal, or antiviral)	IV antibiotic, antifungal, or antiviral intervention indicated; invasive intervention indicated	Life-threatening consequences; urgent intervention indicated	Fatal	
Definition: A disorder characterized by inflammation of the throat.						
Thrush	Asymptomatic; local symptomatic management	Oral intervention indicated (e.g., antifungal)	IV antifungal intervention indicated			
		ed by a suspected can E, Adverse event; IV,	didal infection involvir Intravenous.	ng an oral mucosal s	urface.	
From NCI-CTO	•					

9.8.3. Infections Grade ≥ 3

For this clinical study, severe (Grade \geq 3) infections have been defined as AEIs (see §9.2 for details regarding severity grading).

9.9. Pregnancy

Pregnancies that occur from the time of first study drug dose until the EoS visit, including any pregnancies that occur in the female partner of a male study subject, must be reported to the Sponsor or designee within 48 hours of the Investigator becoming aware of the pregnancy. Pregnancy outcomes of elective or spontaneous abortion, stillbirth, or congenital anomaly, as well as any pregnancy-related events that meet the criteria for an SAE (see §9.3) must be reported as per §9.5.

All pregnancies will be monitored for the full duration; all perinatal and neonatal outcomes should be reported. Refer to the Procedures Manual for complete instructions.

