4. TRIAL DESIGN

4.1. Overview of Study Design

This is a randomized, double-blind, placebo-controlled, parallel-arm study to evaluate the safety, tolerability, efficacy, immunogenicity, PK, of ALPN-101 in adult subjects with chronic, moderate to severe active SLE. Approximately 75 international sites will participate in this study. A total of approximately 130 subjects will be randomized 1:1 to receive a weight-based dose of ALPN-101 or placebo Q2W for a total of 12 doses:

- ALPN-101 at 3 mg/kg (n≈65)
- Placebo (n≈65)

Randomization will be stratified based on SLE treatment at Baseline and geographic region (see §10.2). Subjects will be followed for 4 weeks from the End of Treatment (EoT) visit (i.e., 6 weeks after the last dose of study drug), from the end of Day 155 through Day 197. Assessments of AEs and disease activity, and collection of blood and urine for safety laboratory values, biomarkers of disease activity, PK, ADA, will be performed throughout the study. Refer to the Schedule of Procedures and Assessments (Table 1).

Dense PK samples will be collected in subjects that agree to participate; subjects in this subset will stay in the clinic for 4 hours following administration of the first dose of study drug, and will return to the clinic 1, 3, and 7 days following the first study drug administration for collection of additional samples.

Medications that are used for treatment of SLE at baseline (i.e., hydroxychloroquine/hydroxychloroquine-like drugs, corticosteroids, immunosuppressants) should be maintained at stable doses through the Day 169 assessments, except for incidences of toxicity or for a protocol-defined short-term increase (burst and taper) of corticosteroid dose in response to increased disease activity or reduction in corticosteroids (taper) to reduce toxicity in the context of improvement in disease activity are detailed in §8.2.

Randomization will be stratified by geographic region and will be stratified based on SLE treatment at Baseline (see §10.2).

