- 9. Women of child-bearing potential (WOCBP; defined in APPENDIX 1) or male patients with a WOBCP partner must agree to use highly effective methods of contraception as defined in APPENDIX 1 during study treatment and for 3 months following the last dose of study drug.
- 10. Able to provide written, informed consent.
- 11. Should be up-to-date on all age-appropriate vaccinations, including COVID-19, per local and professional guidelines for immunocompromised individuals (e.g., CDC, local professional society guidelines).
- 12. Peripheral venous access anticipated to be adequate to tolerate planned dosing regimen of IV infusions and blood draws Q2W per Table 1.

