 - g. Estimated glomerular filtration rate (eGFR) < 40 mL/min/1.73m² as assessed by the Chronic Kidney Disease Epidemiology Collaboration (CKD-EPI) creatinine-equation.
- 9. History of new, ongoing, or recurrent malignancy ≤ 5 years prior to first dose of study drug except basal cell carcinoma of the skin, squamous cell skin cancer, or in situ carcinoma that has been adequately treated with no evidence of recurrent disease for ≥ 12 months.
- 10. Pregnant or breastfeeding at the time of screening, or plans to become pregnant \leq 3 months following the last dose of study drug.
- 11. Fulfills diagnostic criteria for another rheumatic disease that overlaps with SLE (e.g., mixed connective tissue disease, overlap connective tissue disease) that may confound clinical

- assessments in the study. However secondary sicca or Sjögren's syndrome or antiphospholipid antibody syndrome that is stable on appropriate therapy is allowed.
- 12. Prior diagnosis of, or fulfills diagnostic criteria for, another autoimmune or inflammatory disease that may confound clinical assessments or increase subject risk in the study, including Behçet's disease, periodic fever syndrome, spondyloarthritis (including psoriatic arthritis, ankylosing spondylitis, reactive arthritis, enteropathic arthritis), inflammatory bowel disease including celiac sprue, or multiple sclerosis. Autoimmune thyroid disease and history of type 1 diabetes are allowed. Other disorders not specifically named are subject to discuss with, and agreement by, the Sponsor or designee.
- 13. Diagnosis of fibromyalgia or fulfills ACR Diagnostic Criteria for Fibromyalgia (e.g., 2010 Preliminary Diagnostic Criteria).
- 14. Functional class IV as defined by the ACR 1991 Revised Criteria for the Classification of Global Functional Status in Rheumatoid Arthritis.
- 15. Medications not intended to be continued during the study period in compliance with Inclusion Criterion 7 must meet the following washout requirements prior to Baseline (i.e., Day 1 prior to randomization):
 - a. Oral or parenteral glucocorticoids: 2 weeks if highest administered dose was 20 mg or less; 4 weeks if highest administered dose was > 20 mg (NOTE: this applies only if corticosteroids are not planned to be continued. See Inclusion Criterion 7 if corticosteroids are planned to be used during the study).
 - b. Cyclophosphamide: 12 weeks.
 - c. Plasmapheresis: 24 weeks.

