6.5. Day 197 (End of Study)

The EoS visit should be scheduled 4 weeks after the EoT visit (Day 169) and should include the following:

- Record AEs and concomitant medications
 - Photography of any oral mucocutaneous lesions reported as AEIs, if applicable
- Perform complete physical examination; obtain vital signs and weight
- Obtain ECG
- Using the provided kit, collect blood and urine samples for safety laboratory evaluations and clinical biomarkers of SLE
- Using the provided kit, collect blood samples for PK /ADA
- Perform urine pregnancy test for WOCBP using the provided kits
- Complete the SDI

NOTE: Additional procedures and/or documentation to support diagnosis of new damage, compared to Baseline, may be required (e.g., radiographic evidence to support diagnosis of avascular necrosis; photography to support new diagnosis of skin damage; other); refer to Procedures Manual

Perform Investigator disease activity assessments: BILAG 2004, SLEDAI-2K 30, PhGA, CLASI.

NOTE: Additional procedures are required to support activity in some organ systems (e.g., confirmation of pleural or pericardial effusion). Refer to Procedures Manual

- Obtain Subject's disease assessments: PtGA, SF-36, FACIT-F (13-item)
- Skin photography, if applicable

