6.6. Unscheduled Visits

6.6.1. Early Termination

If a subject withdraws consent for study participation prior to Day 197, the EoS evaluations should be completed if possible, preferably within 2 weeks of study drug discontinuation. In addition, a follow-up phone call should occur 8 weeks after the last dose of study drug to determine the status of any ongoing AEs/SAEs or the occurrence of any new AEs/SAEs.

As noted in §4.3, subjects who prematurely discontinue treatment with study drug (i.e., due to subject choice, Investigator decision, an AE or other contraindication for ongoing receipt of study drug, etc.), and who do not withdraw consent, should have all procedures outlined in the EoT visit as well as an unscheduled ECG, as soon as possible, preferably within 2 weeks. Afterwards, subjects should resume following the regular visit schedule as outlined in Table 1, and adhere to all study procedures except for study drug dosing. As the subject has discontinued study drug, all concomitant medication restrictions as outlined in §8.2.2 no longer apply. If at any point subsequently a subject no longer wants to provide assessments (withdrawal of consent) following discontinuation of study drug and completion of the EoT assessments, an EoS visit is not required.

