APPENDIX 1 GUIDANCE ON CHILDBEARING POTENTIAL AND HIGHLY EFFECTIVE METHODS OF CONTRACEPTION

Contraceptive Guidance

Investigators shall counsel WOCBP and fertile male participants who are sexually active with WOCBP on the importance of pregnancy prevention and the implications of an unexpected pregnancy. Investigators shall advise these participants on the use of highly effective methods of contraception for WOCBP and will check for adherence during study visits.

Guidance for WOCBP Participants

WOCBP must use a highly effective method of contraception consistently and correctly during the study and for at least 3 months after the last dose of investigational product.

Highly effective methods of contraception have a failure rate of < 1% per year when used consistently and correctly.

The following methods of contraception are considered highly effective:

- Combined hormonal (estrogen + progestin) contraception (oral, intravaginal, transdermal) associated with inhibition of ovulation.
- Progestogen- or progestin-only hormonal contraception (oral, injectable, implantable) associated with inhibition of ovulation.
- Intrauterine device.
- Intrauterine hormone-releasing system.
- Bilateral tubal occlusion.
- Vasectomized partner.
- Sexual abstinence: defined as refraining from heterosexual intercourse during the entire period of risk associated with the study treatments (i.e., during the study and for at least 3 months after the last dose of investigational product). The reliability of sexual abstinence needs to be evaluated in relation to the duration of the clinical study and the preferred and usual lifestyle of the participant.

Guidance for Male Participants with WOCBP Partners

Male participants with a pregnant or non-pregnant WOCBP partner must use a condom during the study and for at least 3 months after the last dose of investigational product. In addition, non-pregnant WOCBP partners of fertile male participants must use a highly effective method of contraception as defined above for WOCBP participants.

Woman of Childbearing Potential

A woman is considered a WOCBP, i.e., fertile, following menarche and until becoming postmenopausal unless permanently sterile.

- Permanent sterilization methods include the following: hysterectomy, bilateral salpingectomy, and bilateral oophorectomy.

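### Protocol 9.9 requires pregnancy reporting only up to the End of Study visit, 6 weeks after the last dose, whereas eligibility and Appendix 1 use 3 months after the last dose.

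*Protocol*

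**What the plan says.** Three places in the protocol look 3 months past the last dose:

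- Section 5.1, Inclusion Criterion 9, requires contraception "during study treatment and for 3 months following the last dose of study drug", for women of childbearing potential and for men with such partners.
- Section 5.2, Exclusion Criterion 10, excludes women planning a pregnancy within "3 months following the last dose of study drug".
- Appendix 1 sets the contraception period as "during the study and for at least 3 months after the last dose of investigational product". In its definition of abstinence it treats this span as the period of risk from study treatment.

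Section 9.9 uses an earlier end point. The duty to report covers "Pregnancies that occur from the time of first study drug dose until the EoS visit", for female subjects and for partners of male subjects. Its next paragraph asks for every pregnancy to be followed through to its outcome, but that concerns follow-up of reported pregnancies and does not lengthen the period in which one must be reported.

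Section 4.1 fixes the distance between the two end points: follow-up runs "from the end of Day 155 through Day 197", which it gives as "6 weeks after the last dose of study drug". For subjects who withdraw from the study, section 6.6.1 places the EoS evaluations "preferably within 2 weeks of study drug discontinuation". The SAP has no rule on pregnancy reporting.

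**The concern.** The protocol asks subjects to avoid pregnancy for 3 months because it regards that time as carrying risk, yet it stops requiring sites to report pregnancies roughly halfway through. If contraception fails in the second half, a site that follows 9.9 to the letter has nothing it must send.

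Safety is the primary objective (section 3.1). Section 4.4.4 describes this as the first study of ALPN-101 in SLE and the first with dosing beyond 4 weeks. Pregnancies will be rare, so each one carries information about a question on which the sponsor has few data.

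No other rule closes the gap:

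- The 8-week telephone call (4.3.2, 6.6.1) asks about adverse events only. It applies to subjects who withdraw or cannot keep attending; completers get no call.
- Section 9.5 allows late serious adverse events judged related to be reported at any time, but that route is optional, and a pregnancy is not in itself serious under 9.3.
- The last scheduled pregnancy test is at EoS (Table 1).
- Section 11.2 provides for partner consent only when the partner conceives while the subject is still taking part.

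**Working it through.** **Inputs.** Last dose Day 155, End of Treatment Day 169, EoS Day 197 (4.1, 6.5, Table 1). Visit windows ±3 days at Days 155 and 197 (Table 1). Five half-lives equated with 8 weeks (4.3.2). The documents give 3 months without a day count; I assume 90 to 92 days.

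**Reproducing the plan's interval.** 197 − 155 = 42 days = 6 weeks, and 197 − 169 = 28 days = 4 weeks. Both match the protocol.

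**Subject dosed on Day 155.** Uncovered days = (3 months) − 42.

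- 90 − 42 = 48 days; 48/90 = 53%.
- 92 − 42 = 50 days; 50/92 = 54%.
- The 3-month period ends on Day 155 + 90 to 92 = Day 245 to 247.
- If 3 months is read as 12 weeks: (84 − 42)/84 = 50%.

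**Effect of visit windows.** Last dose to EoS can be 42 ± 6 = 36 to 48 days. The uncovered share runs from (90 − 48)/90 = 47% to (92 − 36)/92 = 61%.

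**Against the 8-week, five-half-life period.** 155 + 56 = Day 211, and 211 − 197 = 14 days after EoS. That is 14/56 = 25% of the 8 weeks.

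**Withdrawal from the study, EoS evaluations assumed 14 days after the last dose.** 90 − 14 = 76 days (84%); 92 − 14 = 78 days (85%). Even if the 8-week call did elicit pregnancies, 90 − 56 = 34 to 92 − 56 = 36 days (38% to 39%) would remain.

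**Drug stopped early, visits continued to Day 197.** There is no gap if the last dose was on or before Day 197 − 92 = 105 to 197 − 90 = 107.

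**Expected number of events.** SAP 4.1 reports that enrolment stopped at 76. Assume all 76 could become pregnant or have a partner who could, all complete, and contraception fails at 1% per year, the ceiling Appendix 1 gives for correct use. With a 49-day gap: 76 × 49/365 × 0.01 ≈ 0.10 pregnancies, or about 0.05 on ALPN-101 under 1:1 allocation. At ten times that failure rate, the active-arm figure is about 0.5.

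**The case against.** The best case against the point is that contraception is a precaution and reporting is a data-collection rule, and nothing in the protocol says the two must end together. Several parts of this case stand:

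- **Exposure.** A reader might infer that the whole uncovered span is drug exposure. The only exposure figure in the documents is 8 weeks for five half-lives, so only about the first two weeks after EoS fall within it. Days 212 to about 246 belong to the 3-month period but lie beyond five half-lives.
- **Lost data.** A reader might infer that these pregnancies would go uncaptured. The documents support only that reporting is not required. Section 9.9 routes abortion, stillbirth and congenital anomaly through 9.5, which lets related serious events be reported late. Section 9.9 also refers to a Procedures Manual, not available here, which may ask for more.
- **Early stopping.** The 85% figure does not describe everyone who stops drug early. Subjects who only stop treatment are asked to keep their visits, and some of them have no gap.
- **Frequency.** A share of days is not a share of events; well under one pregnancy is expected in the gap.

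What does not stand is that the mismatch is harmless by design. Appendix 1 itself ties the 3 months to risk from treatment, and 9.9 closes even before the protocol's own five-half-life mark for a completer. The 8-week call and the late-event rule reduce the loss without requiring that a pregnancy be reported.

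**Conclusion.** The point holds as an alignment gap of modest consequence. For a subject dosed on Day 155, 48 to 50 of 90 to 92 days (about 54%; 47% to 61% across visit windows) of the protocol's post-dose risk period carry no duty to report a pregnancy. About 14 of those days are also within the 8-week, five-half-life period. The share reaches 84% to 85% for subjects who withdraw from the study, if EoS evaluations fall 2 weeks after the last dose, and is zero for those who stop drug by about Day 106 and remain in follow-up to Day 197.

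These figures rest on reading 3 months as 90 to 92 days and on 9.9 as written, without the Procedures Manual. It would go too far to infer that the primary safety assessment is compromised: few events are expected, and pregnancy is not among the safety endpoints in SAP 3.2. The change is still worth making, because it is cheap and a single pregnancy would be informative.

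**What to change.** Reconcile the passages so that the reporting period and the existing 3-month period agree:

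1. In 9.9, extend the reporting period from the EoS visit to the end of the post-dose period already set in Inclusion Criterion 9 and Appendix 1. For a subject dosed on Day 155 this moves the end from Day 197 to about Day 245 to 247, and the uncovered share falls to zero.
2. At EoS or early termination, remind subjects to tell the site of any pregnancy, including a partner's, that begins in that period.
3. In 11.2, widen the trigger for the pregnant-partner consent form to match. Without this, a partner pregnancy after EoS would be reportable but have no stated consent route.

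The cost is a small wording change to the protocol and possibly the consent forms, with IRB/IEC review, and a few site contacts after EoS. No visit or test is added. Subjects who have withdrawn consent may still not provide the information.
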